**Table 8 Gradings for Urine Analysis Parameters**

Parameter	L1	L2	L3	L4	H1	H2	H3	H4
Urine erythrocytes	NA	NA	NA	NA	≥ULN	≥10 cells/HPF	NA	NA
Urine protein	NA	NA	NA	NA	1+ proteinuria	2+ and 3+ proteinuria; urinary protein <3.5 g/24 hrs	urinary protein ≥3.5 g/24 hrs; 4+ proteinuria	NA
Urine glucose	NA	NA	NA	NA	>ULN (presence of glucose)	NA	NA	NA

LLN: lower limit of normal, ULN: upper limit of normal, NA: not applicable.

Any laboratory parameter with treatment-emergent (i.e., worsening from baseline) abnormalities of grade 2 or above (ie, H2/L2 or higher/lower) should be considered a 'marked laboratory abnormality'. Marked laboratory abnormalities should be described in a corresponding section of the CSR as per ICH E3 guidance, section 12.4.2.3.

**Appendix II: Vital Signs and Electrocardiogram grading****Table 9 Gradings for Vital Signs and Electrocardiogram Parameters**

Parameter	L1	L2	L3	L4	H1	H2	H3	H4
Systolic blood pressure (mmHg)	<90	<60	NA	NA	NA	≥140	≥160	≥180
Diastolic blood pressure (mmHg)	<60	<45	NA	NA	NA	≥90	≥100	≥120
Heart rate (bpm)	<60	<50	<40	NA	>100	>115	>130	NA
Body temperature (°C)	NA	<35	NA	NA	>38	NA	NA	NA
Respiratory rate (breaths per minute)	<12	NA	NA	NA	>20	NA	NA	NA
O 2 saturation (%)	<95	<90	NA	NA	NA	NA	NA	NA
Weight	≥7% decrease from baseline	NA	NA	NA	≥7% increase from baseline	NA	NA	NA
QTc interval on ECG (ms)	NA	NA	NA	NA	>450	>480	>500	NA
QTc change from baseline (ms)	NA	NA	NA	NA	NA	>30	>60	NA
PR interval on ECG (ms)	<110	NA	NA	NA	>200	NA	NA	NA
QRS complex on ECG (ms)	<60	NA	NA	NA	>120	NA	NA	NA

Source: FRM-MED-005/006, valid on 08JUL2020.

## Appendix III: EULAR Sjögren's Syndrome Disease Activity Index (ESSDAI) Score

Domain	Activity level	Description
Constitutional Exclusion of fever of infectious origin and voluntary weight loss	No=0	Absence of the following symptoms
	Low=3	Mild or intermittent fever (37.5–38.5°C)/night sweats and/or involuntary weight loss of 5–10% of body weight
	Moderate=6	Severe fever (>38.5°C)/night sweats and/or involuntary weight loss of >10% of body weight

Domain	Activity level	Description
Articular Exclusion of osteoarthritis	No=0	Absence of currently active articular involvement
	Low=2	Arthralgias in hands, wrists, ankles and feet accompanied by morning stiffness (>30 min)
	Moderate=4	1–5 (of 28 total count) synovitis
	High=6	≥6 (of 28 total count) synovitis

Domain	Activity level	Description
Lymphadenopathy and lymphoma Exclusion of infection	No=0	Absence of the following features
	Low=4	Lymphadenopathy ≥1 cm in any nodal region or ≥2 cm in inguinal region
	Moderate=8	Lymphadenopathy ≥2 cm in any nodal region or ≥3 cm in inguinal region, and/or splenomegaly (clinically palpable or assessed by imaging)
High=12		Current malignant B-cell proliferative disorder

Domain	Activity level	Description
Cutaneous Rate as 'No activity' stable long-lasting features related to damage	No=0	Absence of currently active cutaneous involvement
	Low=3	Erythema multiforma
	Moderate=6	Limited cutaneous vasculitis, including urticarial vasculitis, or purpura limited to feet and ankle, or subacute cutaneous lupus
	High=9	Diffuse cutaneous vasculitis, including urticarial vasculitis, or diffuse purpura, or ulcers related to vasculitis

Domain	Activity level	Description
CNS Rate as 'No activity' stable long-lasting features related to damage or CNS involvement not related to the disease	No=0	Absence of currently active CNS involvement
	Moderate=10	Moderately active CNS features, such as cranial nerve involvement of central origin, optic neuritis or multiple sclerosis-like syndrome with symptoms restricted to pure sensory impairment or proven cognitive impairment
	High=15	Highly active CNS features, such as cerebral vasculitis with cerebrovascular accident or transient ischaemic attack, seizures, transverse myelitis, lymphocytic meningitis, multiple sclerosis-like syndrome with motor deficit

Domain	Activity level	Description
Biological	No=0	Absence of any of the following biological feature
	Low=1	Clonal component and/or hypocomplementemia (low C4 or C3 or CH50) and/or hypergammaglobulinemia or high IgG level between 16 and 20 g/L
	Moderate=2	Presence of cryoglobulinemia and/or hypergammaglobulinemia or high IgG level >20 g/L, and/or recent onset hypogammaglobulinemia or recent decrease of IgG level (<5 g/L)

Domain	Activity level	Description
Pulmonary Rate as 'No activity' stable long-lasting features related to damage, or respiratory involvement not related to the disease (tobacco use, etc)	No=0	Absence of currently active pulmonary involvement
	Low=5	Persistent cough due to bronchial involvement with no radiographic abnormalities on radiography Or radiological or HRCT evidence of interstitial lung disease with: no breathlessness and normal lung function test
	Moderate=10	Moderately active pulmonary involvement, such as interstitial lung disease shown by HRCT with shortness of breath on exercise (NYHA II) or abnormal lung function tests restricted to: 70% $>DL_{CO} \geq 40\%$ or 80% $>FVC \geq 60\%$
	High=15	Highly active pulmonary involvement, such as interstitial lung disease shown by HRCT with shortness of breath at rest (NYHA III, IV) or with abnormal lung function tests: $DL_{CO} <40\%$ or $FVC <60\%$

FVC, forced vital capacity; HRCT, high-resolution CT; NYHA, New York Heart Association.

Domain	Activity level	Description
Haematological For anaemia, neutropenia, and thrombopenia, only auto-immune cytopenia must be considered Exclusion of vitamin or iron deficiency, drug-induced cytopenia	No=0	Absence of autoimmune cytopenia
	Low=2	Cytopenia of autoimmune origin with neutropenia (1000 $<neutrophils < 1500/\text{mm}^3$ ), and/or anaemia (10 $<\text{haemoglobin} < 12 \text{ g/dL}$ ), and/or thrombocytopenia (100 000 $<\text{platelets} < 150 000/\text{mm}^3$ ) Or lymphopenia (500 $<\text{lymphocytes} < 1000/\text{mm}^3$ )
	Moderate=4	Cytopenia of autoimmune origin with neutropenia (500 $\leq \text{neutrophils} \leq 1000/\text{mm}^3$ ), and/or anaemia (8 $\leq \text{haemoglobin} \leq 10 \text{ g/dL}$ ), and/or thrombocytopenia (50 000 $\leq \text{platelets} \leq 100 000/\text{mm}^3$ ) Or lymphopenia ( $\leq 500/\text{mm}^3$ )
	High=6	Cytopenia of autoimmune origin with neutropenia (neutrophils $< 500/\text{mm}^3$ ), and/or anaemia (haemoglobin $< 8 \text{ g/dL}$ ) and/or thrombocytopenia (platelets $< 50 000/\text{mm}^3$ )

Domain	Activity level	Description
Glandular Exclusion of stone or infection	No=0	Absence of glandular swelling
	Low=2	Small glandular swelling with enlarged parotid ( $\leq 3 \text{ cm}$ ), or limited submandibular ( $\leq 2 \text{ cm}$ ) or lachrymal swelling ( $\leq 1 \text{ cm}$ )
	Moderate=4	Major glandular swelling with enlarged parotid ( $> 3 \text{ cm}$ ), or important submandibular ( $> 2 \text{ cm}$ ) or lachrymal swelling ( $> 1 \text{ cm}$ )

Domain	Activity level	Description
Muscular Exclusion of weakness due to corticosteroids	No=0	Absence of currently active muscular involvement
	Low=6	Mild active myositis shown by abnormal EMG, MRI* or biopsy with no weakness and creatine kinase ( $N \leq CK \leq 2N$ )
	Moderate=12	Moderately active myositis proven by abnormal EMG, MRI* or biopsy with weakness (maximal deficit of 4/5), or elevated creatine kinase ( $2N < CK \leq 4N$ )
	High=18	Highly active myositis shown by abnormal EMG, MRI* or biopsy with weakness (deficit $\leq 3/5$ ) or elevated creatine kinase ( $> 4N$ )

\*We decided to add this item not included in the initial version since the value of this examination for the diagnosis of myositis was not clear until recently.  
EMG, electromyogram.

Domain	Activity level	Description	Domain	Activity level	Description
Renal Rate as 'No activity' stable long-lasting features related to damage and renal involvement not related to the disease. If biopsy has been performed, please rate activity based on histological features first	No=0 Low=5 Moderate=10 High=15	Absence of currently active renal involvement with proteinuria <0.5 g/day, no haematuria, no leucocyturia, no acidosis or long-lasting stable proteinuria due to damage Evidence of mild active renal involvement, limited to tubular acidosis without renal failure or glomerular involvement with proteinuria (between 0.5 and 1 g/day) and without haematuria or renal failure (GFR $\geq$ 60 mL/min) Moderately active renal involvement, such as tubular acidosis with renal failure (GFR <60 mL/min) or glomerular involvement with proteinuria between 1 and 1.5 g/day and without haematuria or renal failure (GFR $\geq$ 60 mL/min) or histological evidence of extra-membranous glomerulonephritis or important interstitial lymphoid infiltrate Highly active renal involvement, such as glomerular involvement with proteinuria >1.5 g/day, or haematuria or renal failure (GFR <60 mL/min), or histological evidence of proliferative glomerulonephritis or cryoglobulinemia related renal involvement	PNS Rate as 'No activity' stable long-lasting features related to damage or PNS involvement not related to the disease	No=0 Low=5 Moderate=10 High=15	Absence of currently active PNS involvement Mild active PNS involvement, such as pure sensory axonal polyneuropathy shown by NCS or trigeminal (V) neuralgia *Proven small fibre neuropathy Moderately active PNS involvement shown by NCS, such as axonal sensory-motor neuropathy with maximal motor deficit of 4/5, pure sensory neuropathy with presence of cryoglobulinemic vasculitis, ganglionopathy with symptoms restricted to mild/moderate ataxia, inflammatory demyelinating polyneuropathy (CIDP) with mild functional impairment (maximal motor deficit of 4/5 or mild ataxia) Or cranial nerve involvement of peripheral origin (except trigeminal (V) neuralgia) Highly active PNS involvement shown by NCS, such as axonal sensory-motor neuropathy with motor deficit $\leq$ 3/5, peripheral nerve involvement due to vasculitis (mononeuritis multiplex, etc), severe ataxia due to ganglionopathy, inflammatory demyelinating polyneuropathy (CIDP) with severe functional impairment: motor deficit $\leq$ 3/5 or severe ataxia

GFR, glomerular filtration rate.

\*We decided to add this item not included in the initial version since the link between this entity and SS was not clear until recently.  
CIPD, chronic inflammatory demyelinating polyneuropathy; NCS, nerve conduction study.

## Appendix IV: EULAR Sjögren's Syndrome Patient Reported Index (ESSPRI) Score

1) How severe has your dryness been during the last 2 weeks?

No dryness		Maximal imaginable dryness									
	0	1	2	3	4	5	6	7	8	9	10

[figure not shown]
2) How severe has your fatigue been during the last 2 weeks?

[figure not shown]
No fatigue		Maximal imaginable fatigue									
	0	1	2	3	4	5	6	7	8	9	10

[figure not shown]
3) How severe has your pain (joint or muscular pains in your arms or legs) been during the last 2 weeks?

[figure not shown]
No pain		Maximal imaginable pain									
	0	1	2	3	4	5	6	7	8	9	10

[figure not shown]
Fig. 1. The EULAR Sjögren's Syndrome Patient Reported Index (ESSPRI). The ESSPRI score is the mean of the 3 scales.

[figure not shown]

Galapagos  
GLPG3970-CL-207

**CONFIDENTIAL**

43952\_17306\_34116

[figure not shown]

Galapagos  
GLPG3970-CL-207

**CONFIDENTIAL**

43952\_17306\_34116

## Appendix XI: SAS Code

### Mixed Model for Repeated Measures

The SAS code for MMRM model with unstructured variance-covariance matrix for the primary efficacy endpoint is:

```
PROC SQL data = dataset NOPRINT;
  SELECT mean(AVAL) INTO :b FROM ADXX where paramcd = 'XXX' and fasfl = 'Y'
  and avisit = 'Baseline';
QUIT;
```

For parameters planned to be collected/measured at Week 4, Week 8 and Week 12 the following SAS code will be used:

```
PROC MIXED data = dataset;
  CLASS subjid trt visit ;
  MODEL change = visit*trt bsl*visit/ NOINT DDFM=KenwardRoger;
  REPEATED visit / SUBJECT=subjid TYPE=un;
  LSMEANS visit*trt / cl alpha=0.1 at (bsl) = (&meanbsl. );
  ESTIMATE 'GLPG3970 vs. Placebo: Week 4' avisit*trtp 1 0 0 -1 0 0 /CL ALPHA = 0.1;
  ESTIMATE 'GLPG3970 vs. Placebo: Week 8' avisit*trtp 0 1 0 0 -1 0 /CL ALPHA = 0.1;
  ESTIMATE 'GLPG3970 vs. Placebo: Week 12' avisit*trtp 0 0 1 0 -0 -1 /CL ALPHA = 0.1;
  ESTIMATE 'AUEC GLPG3970' avisit*trtp 4 4 2 0 0 0 bsl*avisit %sysevalf(4*&meanbsl.)
  %sysevalf(4*&meanbsl.)
  %sysevalf(2*&meanbsl.) / divisor = 12 CL ALPHA = 0.1;
  ESTIMATE 'AUEC Placebo' avisit*trtp 0 0 0 4 4 2 bsl*avisit %sysevalf(4*&meanbsl.)
  %sysevalf(4*&meanbsl.)
  %sysevalf(2*&meanbsl.) / divisor = 12 CL ALPHA = 0.1;
  ESTIMATE 'AUEC GLPG3970 vs. Placebo' avisit*trtp 4 4 2 -4 -4 -2 / divisor = 12 CL
  ALPHA = 0.1;
RUN;
```

Code for endpoints measured at Baseline, Week 8 and Week 12:

```
LSMESTIMATE trt*visit
  'GLPG3970 vs Placebo: Week 8' 1 0 -1 0,
  'GLPG3970 vs Placebo: Week 12' 0 1 0 -1;
RUN;
```

For the log transformed parameters the following will be applied:

- In the *PROC SQL*: *AVAL* will be replaced by *log(AVAL)*
- In the *PROC MIXED*:
  - o *Change* will be replaced by *geopchg=log(aval)-log(bsl)*
  - o And *bsl* will be replaced by *log(bsl)*

If the default Newton–Raphson algorithm used by SAS PROC MIXED fails to converge, the following will be tried to avoid lack of convergence while maintaining an unstructured variance:

- A. The Fisher scoring algorithm (via the SCORING option of the PROC MIXED statement) will be used to obtain the initial values of covariance parameters:

*PROC MIXED data = dataset **SCORING=5**;*

...

The rest of the code is the same as the first full proc mixed code provided.

- B. If the above fails, the no-diagonal factor analytic structure will be used which effectively performs the Cholesky decomposition via the TYPE=FA0(V) option of the REPEATED statement, where V is the total number of visits in the response vector (V = 3):

*PROC MIXED data = dataset;*

...

*REPEATED visit / subject=subjid type=FA0(3);*

...

The rest of the code is the same as the first full proc mixed code provided.

- C. If all the above fails, the variance-and-correlations parameterization will be attempted using TYPE =UNR:

*PROC MIXED data = dataset;*

...

*REPEATED visit / subject=subjid type=UNR;*

...

The rest of the code is the same as the first full proc mixed code provided.

In the rare case where all the above fails, the Toeplitz structure with the sandwich variance estimator (EMPIRICAL option) will be used:

*PROC MIXED data = dataset **EMPIRICAL**;*

...

*REPEATED visit / subject=subjid type=TOEP;*

...

The rest of the code is the same as the first full proc mixed code provided.

If this option also fails, the AR(1) + random intercept model will be tried with the sandwich variance estimator:

*PROC MIXED data = dataset **EMPIRICAL**;*

...  
*REPEATED visit / subject=subjid type=AR(1);*  

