**Table 3: Analysis Visit Window for 12-Lead ECG Data**

Visit date and time	Relative day (ADY)	Time window (in ADY)	Target day	Analysis visit (AVISIT)	Analysis time point (ATPT)
Before first study drug administration	<1 or predose at ADY=1	<1 or predose at ADY=1	1	Baseline	
Same as or after first study drug administration	$\geq 1$	1	1	Day 1	As indicated in the database: 1.5, 3, 4.5 hours postdose
		2 to 19	8	Week 1	Predose
		20 to 43	29	Week 4	Predose
		44 to 71	57	Week 8	Predose
		72 to 92	85	Week 12	Predose
		>7 days after last dose of IP	Last dose of IP + 28 days	Follow-up *	

\* The Follow-up window has precedence over all other time windows.

[figure not shown]
**Note:** At baseline and Day 1 predose and 4.5 hours postdose, triplicate ECGs will be recorded. At all other timepoints, single ECGs will be taken.

Table 4: Analysis Visit Window for PK Data

Visit date and time	Relative day (ADY)	Time window (in ADY)	Target day	Analysis visit (AVISIT)	Analysis time point (ATPT)
Before first study drug administration	<1 or predose at ADY=1	<1 or predose at ADY=1	1	Baseline	Predose (within 30 minutes prior to dosing)
Same as or after first study drug administration	$\geq 1$	1	1	Day 1	As indicated in the database: 0.5-1.5, 2-2.5, 4.5 hours postdose
		2 to 19	8	Week 1	As indicated in the database: Predose
		20 to 43	29	Week 4	As indicated in the database: Predose
		44 to 71	57	Week 8*	As indicated in the database: Predose, 0.5-1.5, 2-2.5 hours postdose
		72 to 92	85	Week 12	As indicated in the database: Predose
		>2 days after last dose of IP	Last dose of IP+28 days	Follow-up**	

\*If postdose week 8 is missing and postdose week 12 are available, it means these postdose week 12 will be considered as postdose week 8, that records will be presented in week 8 in tables (with footnote) and with flagged in listings

\*\*The Follow-up window has precedence over all other time windows.

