### 6.2.2. Primary Efficacy Parameter

The primary efficacy endpoints for this study is the change from baseline in ESSDAI score at Week 12.

The ESSDAI is a systemic disease activity index to assess 12 domains (i.e. organ systems: constitutional, lymphadenopathy, glandular, articular, cutaneous, pulmonary, renal, muscular, peripheral nervous system, CNS, hematological, biological) in patients with pSS, where each of the domains is divided into 3-4 levels of activity. These scores are summed across the 12 domains in a weighted manner to provide the total score (range 0-123). A clinically meaningful reduction from baseline ( $\geq 3$  points) indicates the improvement of symptoms.

The ESSDAI will be assessed at baseline, week 4, week 8 and week 12.

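### The Appendix XI MMRM template cannot run as printed, and repairing it on text AVISIT could silently put the Week 8 difference under the Week 12 label

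*SAP*

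**What the plan says.** SAP 6.2.2 sets the target: "The primary efficacy endpoints for this study is the change from baseline in ESSDAI score at Week 12". Section 6.2.2.2 asks for the least-squares mean difference, its two-sided 90% CI and a p-value from an MMRM. SAP Section 1 keeps the primary endpoint analysis after the early termination.

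Appendix XI gives the code for parameters measured at Weeks 4, 8 and 12 and presents it as the code to be applied:

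- The procedure is called with "PROC MIXED data = dataset" and no ORDER= option, here or in the printed lines of any fallback.
- The class variables are "CLASS subjid trt visit" and the model line is "MODEL change = visit*trt bsl*visit/ NOINT DDFM=KenwardRoger". REPEATED and LSMEANS also use `visit`, and LSMEANS uses `trt`.
- The treatment differences come from positional rows on a different pair of names: "ESTIMATE 'GLPG3970 vs. Placebo: Week 4' avisit*trtp 1 0 0 -1 0 0 /CL ALPHA = 0.1", a matching Week 8 row, and "ESTIMATE 'GLPG3970 vs. Placebo: Week 12' avisit*trtp 0 0 1 0 -0 -1 /CL ALPHA = 0.1". The AUEC rows use weights 4 4 2 with divisor 12.
- The preceding PROC SQL step selects the baseline mean with "and avisit = 'Baseline", so AVISIT is treated there as text. It stores the mean as `:b`, but the model step calls `&meanbsl.`.

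SAP Tables 3 and 4 (ECG and PK windows) have a column "Analysis visit (AVISIT") with the values Week 1, Week 4, Week 8 and Week 12, without leading zeros.

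**The concern.** The LSMEANS statement requests no differences, so in this template the primary estimate, its CI and its p-value come only from the ESTIMATE rows. Those rows pick cells by position, and nothing in the code fixes the order of the visits.

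The name mismatch has to be repaired before the code can run. One natural repair is to put `avisit` and `trtp` in CLASS and MODEL, because those are the names in the ESTIMATE rows and AVISIT is the analysis-visit variable shown in the SAP. That removes the visible fault but can leave a silent one: the job runs, and each row prints under the label typed for it, whichever visit it actually picks. At stake is whether the figure reported as the Week 12 difference is the Week 12 difference.

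**Working it through.** **Inputs.** Contrast vectors, CLASS order and AUEC weights: SAP Appendix XI. Visit labels: SAP Tables 3 and 4. Treatment labels: SAP 4.5.1. Assumed, because the documents do not state it: PROC MIXED without ORDER= sorts class levels by formatted value, and the CLASS order makes treatment the slow index and visit the fast one.

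**1. Order intended by the author.** The plan's own AUEC weights settle this. Write W4, W8 and W12 for the values at the three visits. The trapezoidal rule on weeks 0, 4, 8, 12, with change = 0 at baseline, gives

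2(0 + W4) + 2(W4 + W8) + 2(W8 + W12) = 4·W4 + 4·W8 + 2·W12, divided by 12.

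This reproduces 4 4 2 / 12, so the vectors assume Week 4, Week 8, Week 12.

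**2. Order under a text sort.** The labels first differ at the character after the space: 1, 4 or 8. The sorted order is Week 12, Week 4, Week 8. For treatment, GLPG3970 400 mg qd sorts before Placebo, so the sign of the contrasts is right either way.

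**3. What each row picks.**

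| Row label | Vector | Chronological levels | Text levels |
|---|---|---|---|
| Week 4 | 1 0 0 −1 0 0 | Week 4 | Week 12 |
| Week 8 | 0 1 0 0 −1 0 | Week 8 | Week 4 |
| Week 12 | 0 0 1 0 0 −1 | Week 12 | **Week 8** |
| AUEC, W4:W8:W12 | 4 4 2 −4 −4 −2 | 4:4:2 | 4:2:4 |

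In the two-visit LSMESTIMATE code, Week 12 sorts before Week 8, so its two labels swap.

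**4. Size.** Let D8 and D12 be the true treatment differences at Weeks 8 and 12.

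- Primary row: reported − true = D8 − D12.
- AUEC: with weights 4:2:4 instead of 4:4:2, reported − true = (2·D12 − 2·D8)/12 = (D12 − D8)/6.

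Range for the primary row, using as assumed effects the reference values −2, −3 and −5 from SAP 2.6:

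| D8 | D12 | Reported as Week 12 | Error |
|---|---|---|---|
| −3 | −3 | −3 | 0 |
| −2 | −3 | −2 | 1 |
| −2 | −5 | −2 | 3 |

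AUEC with assumed differences −1, −2, −3 at Weeks 4, 8, 12: the correct value is (4·(−1) + 4·(−2) + 2·(−3))/12 = −1.50. Under text order it is (4·(−3) + 4·(−1) + 2·(−2))/12 = −1.67.

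**5. Check by fitting.** A generalised least-squares fit to one simulated data set (20 versus 10 subjects) gave differences of −2.171, −0.717 and −2.813 at Weeks 4, 8 and 12 with chronological levels. With text levels and the same vectors, the row labelled Week 12 returned −0.717, Week 4 returned −2.813 and Week 8 returned −2.171. AUEC moved from −1.431 to −1.781. This confirms the mapping; it does not predict the trial's result.

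**The case against.** A reader might infer that the template, as written, returns the Week 8 difference. The documents do not support that. As printed, the ESTIMATE rows name variables that are in neither CLASS nor MODEL, so they cannot work until someone edits them. The SAP does not say whether `visit` is text or numeric, and SAP Section 1 puts technical derivation details in a separate document, so a numeric companion to AVISIT cannot be ruled out. The efficacy visit-window table is not visible in the text available, so the labels are taken from the ECG and PK tables. With an unformatted numeric visit variable, every row is right.

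The code is also plainly a skeleton, with placeholder dataset and parameter names. The intended quantity is clear from Sections 6.2.2 and 6.2.2.2. The LSMEANS output is labelled by level, and Section 6.2.2.2 requires the means to be shown with the difference, so a careful reader could see that the Week 12 difference did not match the gap between the Week 12 means.

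All of this stands, and it lowers the severity. It does not remove the defect: the appendix presents the code as what will be applied, the code must be edited, one natural edit gives a wrong label on the primary row without an error message, and the SAP requires no comparison of ESTIMATE with LSMEANS.

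The side effects carry little weight. After early termination, provisions no longer applicable are marked by grey shading that the available text does not show, so it is unclear whether AUEC and the two-visit code are still in use. The Toeplitz and AR(1) fallbacks, which would treat Week 12 and Week 4 as adjacent under text order, apply only if every unstructured attempt fails.

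**Conclusion.** The concern holds in conditional form. Two statements are firm: the template cannot run as printed, and its contrasts are correct only for levels ordered Week 4, 8, 12. The wrong-visit result needs two further conditions: that the names are harmonised on text AVISIT, and that the default level ordering applies. Then the Week 12 row carries the Week 8 difference with its CI and p-value. The error is D8 − D12: nothing if the effect is the same at both visits, and as large as the change in effect between them otherwise. Under the unstructured covariance the model fit itself is unaffected; only the attachment of contrasts to visits is. This is a should-fix programming specification, not evidence that a wrong result was or will be produced.

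**What to change.** In Appendix XI:

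1. Use one unformatted numeric visit variable (for example AVISITN = 4, 8, 12) and one treatment variable in CLASS, MODEL, REPEATED, LSMEANS and ESTIMATE, keeping treatment before visit in CLASS. Alternatively, use non-positional LSMESTIMATE syntax that names the level.
2. Do not rely on ORDER=INTERNAL with text AVISIT, because the internal values are the same text and sort the same way. ORDER=DATA depends on the record order of both visit and treatment. A numeric variable carrying a Week n display format would also sort wrongly under the default.
3. Use one macro variable name for the mean baseline, and remove the data= option from PROC SQL.
4. If the two-visit code is still in use, apply the same visit variable there and add CL ALPHA=0.1.
5. Require that each ESTIMATE difference equals the difference between the corresponding labelled LSMEANS before results are released.

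The cost is a few lines of template code and one programming check. The estimand, the model and the data collected do not change.
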